5. TREATMENT OF SUBJECTS

STUDY PHASE 1

After informed consent is obtained, a single dry electrode cap EEG (see chapter 6) will be performed in each patient. We will compare the regular EEG to the dry electrode cap EEG and collect information on patient characteristics, medical history and medication use. There are no follow up visits.

STUDY PHASE 2

After informed consent is obtained, a single dry electrode cap EEG (see chapter 6) will be performed in each patient. Additionally we will collect information on patient characteristics, medical history, medication use, physical and neurological examination performed by the treating physician, imaging studies, diagnosis and treatment, obtained from the patient and the treating physician. There are no follow up visits.

STUDY PHASE 3

Directly at presentation in the ER, a single dry electrode cap EEG (see chapter 6) will be performed in each patient. As soon as feasible, preferably within 72 hours after arrival at the hospital or at discharge (whichever comes first), informed consent is asked (deferred consent, see chapter 10). If informed consent is obtained, we will collect information on patient characteristics, medical history, medication use, physical and neurological examination performed by the treating physician, imaging studies, diagnosis and treatment as well as logistical and technical information, obtained from the patient, the EMS and the treating physician. There are no follow up visits.

STUDY PHASE 4

In the ambulance, a single dry electrode cap EEG (see chapter 6) will be performed in each patient. As soon as feasible, preferably within 72 hours after arrival at the hospital or at discharge (whichever comes first), informed consent is asked (deferred consent, see chapter 10). If informed consent is obtained, we will collect information on patient characteristics, medical history, medication use, physical and neurological examination performed by the treating physician, imaging studies, diagnosis and treatment as well as logistical and technical information, obtained from the patient, the EMS and the treating physician. There are no follow up visits.

6. INVESTIGATIONAL PRODUCT

This is not applicable, since no investigational product(s) will be used in this study.

7. NON-INVESTIGATIONAL PRODUCT

7.1 NAME AND DESCRIPTION OF NON-INVESTIGATIONAL PRODUCT

We plan to use the Waveguard™ dry electrode EEG cap and compatible eego™ amplifiers, developed by ANT Neuro B.V. Netherlands and all CE marked as medical devices in the European Union (see appendices 1 and 2). The dry electrode cap records the EEG signal; the amplifier is used to amplify the EEG signal and reduce artefacts. All products will be used within the intended use as described in the user manuals (see appendices 5, 6, 7, 8 and 9). We will use CE marked NeuroCenter® EEG software (CE class IIa) from Clinical Science Systems (ISO 9001 and ISO 13485 certified) and CE marked eego™ software (CE class IIa) from ANT Neuro B.V. to acquire the signals from the eego™ compatible amplifiers (see appendix 3 and 4).

In a subgroup of patients, who will be included in study phase 3, we plan to use Ambu® Neuroline 720 electrodes together with the Refa multichannel amplifier by TMSi (Twente Medical Systems International B.V. Netherlands), which are CE marked as medical devices in the European Union (see appendices 10 and 11). The electrodes record the EEG signal; the amplifier is used to amplify the EEG signal and reduce artefacts. All products will be used in accordance with the intended use as described in the user manuals (see appendices 12 and 13).

7.2 SUMMARY OF FINDINGS FROM NON-CLINICAL STUDIES

This is not relevant for the Waveguard™ dry electrode cap, eego™ amplifier, Neuroline 720 electrodes and Refa amplifier as they are all CE marked products that have been safely used in clinical studies (see chapter 7.3). NeuroCenter® EEG software and the eego™ software are both a CE class IIa product.

7.3 SUMMARY OF FINDINGS FROM CLINICAL STUDIES

The Waveguard™ dry electrode cap, eego™ amplifier, Neuroline 720 electrodes and Refa amplifier have all been safely used in several clinical studies, with no reported adverse events²²⁻³¹. A small clinical study has shown that the Waveguard's signal quality is similar to that of the conventional 128-channel wet (gel/paste) EEG²². However, to our knowledge, no study of the diagnostic accuracy of dry electrode cap EEG (or EEG in general) for LVO-a has been performed.

7.4 SUMMARY OF KNOWN AND POTENTIAL RISKS AND BENEFITS

The benefit of using either a dry electrode EEG cap or Neuroline 720 electrodes is that they are easily applicable and drastically reduce preparation time, which makes them suitable for use in an emergency setting. Since EEG is a safe, non-invasive and painless procedure that is used regularly in standard medical practice and we will use CE marked products for our measurements, we expect no health risks and no to minimal discomfort during a short period of time associated with participation³². The dry electrode EEG caps will be cleaned and disinfected as recommended in the user manual (appendix 5) and the disposable Neuroline 720 electrodes will be for single use only.

8. METHODS

8.1 STUDY PARAMETERS/END POINTS

8.1.1 MAIN STUDY PARAMETER/END POINT

The primary end point of the study is the area under the ROC curve of the theta/alpha ratio for diagnosis of LVO-a, based on dry electrode EEG performed by paramedics in the ambulance in suspected AIS patients.

8.1.2 SECONDARY STUDY PARAMETERS/END POINTS

Secondary end points of this study are:

- Sensitivity, specificity, PPV and NPV of the theta/alpha ratio, and test characteristics of other existing EEG data based algorithms for LVO-a detection (e.g. Weighted Phase Lag Index, delta/alpha ratio);
- Logistical and technical feasibility of paramedics performing dry electrode cap EEG in the ambulance in suspected AIS patients;
- Developing one or more novel EEG data based algorithms with an optimal diagnostic accuracy for LVO-a detection in suspected AIS patients with ambulant dry electrode cap EEG.

8.2 BLINDING

In this diagnostic accuracy study, the treating clinical team (in all phases) and the paramedics (in phase 4) are blinded for the outcome of the EEG.

8.3 STUDY PROCEDURES

All collected data and study procedures are listed per study phase in the following table. There are no follow up visits. Items that are **not** part of standard medical procedure/treatment are bold.

	Phase 1	Phase 2	Phase 3	Phase 4
Patient characteristics*	At baseline	At baseline	<24 hours after arrival in hospital or at discharge (whichever comes first)	<24 hours after arrival in hospital or at discharge (whichever comes first)
Past medical history	At baseline	At baseline	<24 hours after arrival in hospital or at discharge (whichever comes first)	<24 hours after arrival in hospital or at discharge (whichever comes first)
Medication use	At baseline	At baseline	<24 hours after arrival in hospital or at discharge (whichever comes first)	<24 hours after arrival in hospital or at discharge (whichever comes first)
Pre-stroke modified Rankin Scale score	NA	At baseline	<24 hours after arrival in hospital or at discharge (whichever comes first)	<24 hours after arrival in hospital or at discharge (whichever comes first)
Physical and neurological examination by treating physician	NA	At arrival in ER, data collected retrospectively at baseline	At arrival in ER	At arrival in ER
National Institute of	NA	At arrival in ER, data	At arrival in ER	At arrival in ER

Health Stroke Scale (NIHSS) score	collected retrospectively at baseline			
Brain imaging results, if available	NA	At arrival in ER, data collected retrospectively at baseline	At arrival in ER (if necessary, as judged by treating physician)	At arrival in ER (if necessary, as judged by treating physician)
Dry electrode cap EEG	At baseline	At baseline	At arrival in ER	At arrival of ambulance
Final diagnosis, as judged by treating physician	NA	At baseline	At discharge	At discharge
Treatment with IVT and/or EVT	NA	Data collected retrospectively at baseline	At arrival in ER (if necessary, as judged by treating physician)	At arrival in ER (if necessary, as judged by treating physician)
Times regarding stroke logistics**	NA	Data collected retrospectively at baseline	Collected during first 24 hours after symptom onset	Collected during first 24 hours after symptom onset

*Age, sex, right/left-handedness, estimated quantity and length of hair on the head of the participant.

**Time of: last seen well or witnessed stroke onset, 112-call, ambulance arrival on site, ambulance departure to hospital, ambulance arrival at hospital, start neuro-imaging (if any), start IVT/EVT (if any), transfer times from other primary hospital (if applicable).

8.4 WITHDRAWAL OF INDIVIDUAL SUBJECTS

Subjects can leave the study at any time for any reason if they wish to do so without any consequences.

The investigator can decide to withdraw a subject from the study for urgent medical reasons.

8.5 REPLACEMENT OF INDIVIDUAL SUBJECTS AFTER WITHDRAWAL

Since our sample size calculation includes an expected dropout rate, we will not replace subjects that have withdrawn from the study. Record will be kept of all reasons for withdrawal and these will be reported along with the study results.

9. SAFETY REPORTING

9.1 TEMPORARY HALT FOR REASONS OF SUBJECT SAFETY

In accordance to section 10, subsection 4, of the WMO, the sponsor will suspend the study if there is sufficient ground that continuation of the study will jeopardise subject health or safety. The sponsor will notify the accredited METC without undue delay of a temporary halt including the reason for such an action. The study will be suspended pending a further positive decision by the accredited METC. The investigator will take care that all subjects are kept informed.

9.2 AES, SAES AND SUSARS

9.2.1 ADVERSE EVENTS (AES)

Adverse events are defined as any undesirable experience occurring to a subject during the study, whether or not considered related to the investigational product or the intervention. All adverse events reported spontaneously by the subject or observed by the investigator or his/her staff will be recorded.

9.2.2 SERIOUSADVERSE EVENTS (SAES)

A serious adverse event is any untoward medical occurrence or effect that:

- results in death;
- is life threatening (at the time of the event);
- requires hospitalisation or prolongation of existing inpatients' hospitalisation;
- results in persistent or significant disability or incapacity;
- any other important medical event that did not result in any of the outcomes listed above due to but could have been based upon appropriate judgement by the investigator.

The sponsor will report the SAEs through the web portal *ToetsingOnline* to the accredited METC that approved the protocol, within 15 days of first knowledge of the SAE.

Stroke often results in complications such as infections, delirium, constipation, decubitus wounds, swallowing difficulties and falls, as well as in hospitalization and death. Because we expect no health risk related to participation in this study, these events will be reported to the accredited METC that approved the protocol in a yearly line listing until the last patient has completed the study.

Furthermore, the following situations will not be reported as (S)AEs:

- Elective hospitalization for pre-existing conditions that have not been exacerbated by study treatment as judged by the clinical investigator and where admission did not take longer than anticipated;
- Admission for diagnosis or therapy of a condition that existed before inclusion to this study and has not increased in severity or frequency as judged by the clinical investigator;
- Anticipated day-to-day fluctuations of pre-existing disease(s) or condition(s) present at the start of the study that do not worsen.

9.3 FOLLOW UP OF ADVERSE EVENTS

All AEs will be followed until they have abated, or until a stable situation has been reached. Depending on the event, follow up may require additional tests or medical procedures as indicated, and/or referral to the general physician or a medical specialist. SAEs will be reported if they occur within 1 hour after completion of the EEG-measurement.

9.4 SAFETY COMMITTEE

Installation of a safety committee is not deemed necessary, considering that EEG is a safe, non-invasive and painless procedure that is used regularly in standard medical practice and we are using CE marked products only.

10. STATISTICAL ANALYSIS AND ALGORITHM DEVELOPMENT

STUDY PHASE 1 AND 2

For phase 1 and 2 of this study, the obtained data will not be statistically analyzed, for these phases are meant to gain technical and logistical information on the products being used in a non-emergency setting.

STUDY PHASE 3

For phase 3 of this study, we will determine the diagnostic accuracy of several existing and one or more self-developed EEG data based algorithms for LVO-a detection by comparing the proportions of patients with and without an LVO-a as predicted by EEG to the proportion of patients with and without an LVO-a as diagnosed by the treating physician. A receiver operating characteristic (ROC) curve will be plotted for each algorithm and the optimal cut-off value for each algorithm will be determined. For these cut off values, the sensitivity, specificity, negative predictive value and positive predictive value will be reported with 95% confidence intervals.

ALGORITHM DEVELOPMENT

Data of phase 3 and phase 4 will be used to develop one or more new EEG based algorithms for LVO-detection. We will create artificial intelligence (AI) based algorithm(s). First, we will create a logistic

regression model based on standard EEG features, e.g. time domain characteristics, power spectral density in different frequency bands, coherence measures, and entropy measures. This will be the reference to assess the improvement of the novel AI based models. Second, we will work on EEG classification algorithms based on random forests and support vector machines, using the same EEG features as input. Finally, to support future studies, we will explore new methods that use raw EEG data as input, such as convolutional or recurrent neural networks³³⁻³⁵.

STUDY PHASE 4

For phase 4 of this study, we will determine the diagnostic accuracy of several existing and one or more self-developed EEG data based algorithms for LVO-a detection by comparing the proportions of patients with and without an LVO-a as predicted by EEG to the proportion of patients with and without an LVO-a as diagnosed by the treating physician. An ROC curve will be plotted for each algorithm and the optimal cut-off value will be determined. For this cut off value, the sensitivity, specificity, negative predictive value and positive predictive value will be reported with 95% confidence intervals.

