For study phase 4, where we aim to validate existing algorithms and one or more new algorithms for LVO-a detection, our primary outcome measure is the specificity of the dry electrode cap EEG in a population of patients with a suspected AIS. Sample size calculation is based on an expected specificity of 70% for LVO-a. Originally, sample size calculation was based on an expected LVO-a rate of 7% and a dropout rate of 20%. However, an interim analysis, based on 137 suspected stroke patients in whom an EEG was performed in the ambulance, showed an actual incidence of LVO-a of 5% and a dropout rate of 58%. Patients considered as a 'drop out' had insufficient EEG data quality (n=72), onset of symptoms >24 hours before EEG registration (n=4) or did not give consent for participation in the study (n=3). The EEG data quality increased over the course of the study, so we expect a lower dropout rate for future EEG registrations. Based on these interim data, we adjusted the sample size for phase 4 of the study as follows.

With an incidence of LVO-a of 5% among patients with a clinically suspected AIS in the ambulance, an alpha of 0.05, and a maximum margin of error of 7%, 174 patients with a suspected AIS are required²¹. Assuming a dropout rate of 55%, we intend to recruit 386 patients with a suspected AIS. A patient is considered a 'drop out' if no informed consent is/can be obtained, if no information on the diagnosis made by the treating physician is/can be obtained, or if the EEG measurement is of insufficient technical quality, as judged by the clinical neurophysiologist. Patients included in the 'run in' phase are excluded from the primary analysis and thus not included in our sample size calculation. In the 'run in' phase, we will additionally include 50 patients or less.

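### Section 10 sets out to assess improvement over a reference model, but its stated outputs are values at each algorithm's own cut-off, with no paired comparison and AUC prespecified only for the theta/alpha ratio

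*Combined protocol and SAP*

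**What the plan says.** Section 10, phase 3: "A receiver operating characteristic (ROC) curve will be plotted for each algorithm and the optimal cut-off value for each algorithm will be determined". Then: "For these cut off values, the sensitivity, specificity, negative predictive value and positive predictive value will be reported with 95% confidence intervals". Phase 4 follows the same scheme: "An ROC curve will be plotted for each algorithm and the optimal cut-off value will be determined". No criterion for the optimal cut-off is given in either phase.

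A comparison is nevertheless intended. Under the algorithm development heading, section 10 says of the logistic regression model: "This will be the reference to assess the improvement of the novel AI based models". Section 8.1.2 lists as a secondary end point: "Developing one or more novel EEG data based algorithms with an optimal diagnostic accuracy for LVO-a detection".

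A measure that does not depend on a cut-off is named once, in section 8.1.1, for one algorithm: "The primary end point of the study is the area under the ROC curve of the theta/alpha ratio for diagnosis of LVO-a". For the rest, section 8.1.2 promises "test characteristics of other existing EEG data based algorithms for LVO-a detection", without saying that these include the AUC. Section 3 specifies a single EEG per patient, so all algorithms within a phase are evaluated on the same recordings. Section 1 ranks specificity above sensitivity, but the cut-off rule does not refer to this.

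**The concern.** The stated outputs do not match the comparison that section 10 announces, for two reasons.

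First, two algorithms can have the same ROC curve and still show different sensitivity and specificity if they are cut at different points. A table at each algorithm's own cut-off therefore cannot separate better accuracy from a different trade-off.

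Second, the algorithms are computed on the same patients. An interval for each algorithm describes that algorithm correctly, but does not give the uncertainty of a difference between two of them. That depends on the within-patient correlation, which the planned outputs do not use.

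Without a stated measure, the basis for saying that an AI model improves on the logistic regression would be chosen after the results are seen. A genuine gain could also be missed because the available intervals are too wide for the question. This affects secondary aims. The primary end point, the AUC of a single named ratio, is untouched.

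**Working it through.** **1. Inputs and the plan's own figures.** Phase 3 (section 4.4): 60 / 0.20 = 300 patients, 60 with LVO-a and 240 without. Phase 4 (section 4.4): expected specificity 70%, margin 7%, alpha 0.05, LVO-a incidence 5%. The number without LVO-a is 1.96² × 0.70 × 0.30 / 0.07² = 164.6, and 164.6 / 0.95 = 173.3, rounded up to 174 as stated. With 55% dropout, 174 / 0.45 = 386.7, against 386 stated. Expected LVO-a cases are 174 × 0.05 = 8.7, so about 9 with and 165 without. Phase 4 is sized for the precision of one specificity, and phase 3 to reach 60 LVO-a cases. Neither is sized for a difference between algorithms.

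The documents give no expected AUC and no correlation between algorithms. Both are assumptions below.

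**2. Operating point against accuracy.** On an equal-variance binormal curve, sensitivity = Φ(√2·Φ⁻¹(AUC) − Φ⁻¹(specificity)). With AUC 0.80, √2 × 0.842 = 1.190, which gives:
- specificity 70%: Φ(1.190 − 0.524) = 75%
- specificity 80%: Φ(1.190 − 0.842) = 64%
- specificity 90%: Φ(1.190 − 1.282) = 46%

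Accuracy is identical in all three cases. Only the cut-off moves.

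**3. Pairing, for a proportion.** Take specificities of 70% and 78% in the 240 phase 3 patients without LVO-a. The separate 95% intervals are 64.2% to 75.8% and 72.8% to 83.2%, and they overlap. The paired difference has SE = √[(b + c − d²)/n], where b and c are the discordant proportions and d = b − c = 0.08.
- c = 0.01, b = 0.09: SE = √[(0.10 − 0.0064)/240] = 0.020, interval 4.1 to 11.9 points.
- c = 0.10, b = 0.18: SE = √[(0.28 − 0.0064)/240] = 0.034, interval 1.4 to 14.6 points.
- Treated as independent: 0.2 to 15.8 points.

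The independent interval also just excludes zero, so part of the problem is reading overlap as absence of a difference. Pairing adds the gain in width.

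**4. Pairing, for the AUC.** SE(difference) = √(SE₁² + SE₂² − 2r·SE₁·SE₂). In simulations of two equally accurate algorithms (bivariate binormal scores, AUC 0.75 or 0.80, within-class score correlation 0.5 or 0.7), with half-width = 1.96 × SE:

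| | SE, paired | SE, as if independent | 95% half-width, paired | 95% half-width, independent |
|---|---|---|---|---|
| Phase 3 (60/240) | 0.026–0.036 | 0.043–0.050 | 0.05–0.07 | 0.08–0.10 |
| Phase 4 (about 9/165) | 0.06–0.085 | 0.10–0.12 | 0.12–0.17 | 0.20–0.24 |

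Hanley-McNeil standard errors for AUC 0.80 against 0.85 agree in size. In phase 3 the half-width is 0.095 at r = 0 and 0.067 at r = 0.5. In phase 4 it is 0.238 and 0.169.

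**5. What the planned table would show.** In the same phase 3 simulations, with each algorithm cut at its own Youden point (an assumption, since section 10 names no rule), one of two equally good algorithms is better on sensitivity and the other on specificity in about four runs of five. The planned table then gives no order. Sensitivities differ by 10 points or more in:
- roughly 42% to 53% of runs when the cut-offs are re-estimated in each study
- 11% to 18% when they are fixed beforehand at the true Youden point
- 15% to 25% at a common empirical specificity of 70%

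In phase 4, sensitivity at a common 70% specificity still differs by 10 points or more in 69% to 76% of runs, because one case among 9 is worth 11 points.

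**The case against.** The strongest reply is that section 10 plots an ROC curve for every algorithm in both phases. Such a curve shows sensitivity at every specificity, its area does not depend on the cut-off, and AUC is already the primary measure. A reader might infer that the algorithms cannot be ranked at all. The documents do not support that: the material for ranking is there, and what is missing is a statement of which summary is used and how differences are estimated.

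Three other strong readings also fail.
- A reader might infer that a single best algorithm must be named. Section 8.1.2 asks for one or more novel algorithms and selects no winner. The explicit comparison is that of the AI models with the logistic regression.
- A reader might infer that the plan compares algorithms by their separate intervals. Section 10 says no such thing. It is silent on method, and the separate intervals are right for describing each algorithm.
- A reader might take the 42% to 53% in step 5 as the size of this problem. Most of it is noise from estimating cut-offs in the data, which is a different matter. With cut-offs fixed beforehand at a comparable point it falls to 11% to 18%, no worse than at a common specificity.

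It is also fair to say that own cut-offs need not give different trade-offs, and that the 70% in section 4.4 ("Sample size calculation is based on an expected specificity of 70% for LVO-a") is a planning value for precision, not a target for every algorithm.

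What stands is that an ROC plot without a stated summary or an interval for the difference does not carry out the assessment of improvement that section 10 announces.

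**Conclusion.** The point holds as a gap in the analysis of secondary aims. Section 10 intends a comparison on the same patients, but specifies neither a measure for it, nor a common operating point, nor a paired interval. AUC is prespecified for the theta/alpha ratio only.

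The gain from closing the gap is clearest in phase 3, where pairing cuts the standard error of an AUC difference by roughly 25% to 42%. These figures rest on assumed AUCs of 0.75 to 0.80, score correlation of 0.5 to 0.7 and the full 60/240 patients. Section 4.4 allows fewer, and lower correlation would shrink the gain.

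In phase 4, about 9 LVO-a cases leave a paired half-width of 0.12 to 0.17 in AUC, and a common specificity barely steadies sensitivity. Comparisons between algorithms there can only be exploratory.

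**What to change.** In section 10, for phases 3 and 4, add that:
- the AUC of every algorithm is reported with a 95% interval;
- any comparison with the logistic regression reference, or between algorithms, rests on the paired difference in AUC with a 95% interval (DeLong or patient-level bootstrap), and not on the values at each algorithm's own cut-off;
- this is supported by sensitivity at one prespecified common specificity, with its paired difference. The investigators choose the value in advance, in line with the priority for specificity in section 1;
- comparisons in phase 4 are labelled exploratory because of the small number of LVO-a cases.

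For models fitted to study data, the paired difference should use held-out or cross-validated predictions from the same patients for both models. The planned values at each algorithm's own cut-off can stay as description.

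The cost is a few lines of text and a short extra computation on data already held, with no additional patients or measurements. It does not remedy the low precision in phase 4.
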